Sponsor's co-ordinator	[name], Research Facilitator R&D Department Southampton General Hospital [name] United Kingdom [contact] E-mail: [contact]
Funder(s) Fisher & Paykel Healthcare	Fisher & Paykel Healthcare Limited [name] United Kingdom
Key Protocol Contributors [name]	[contact]

STUDY SUMMARY

Study Title	Preoxygenation of the lungs with high-flow nasal oxygen using Optiflo™ - does speech have an effect on end-tidal oxygen w achieved when compared to closed-mouth nasal breathing?
-------------	---

Short title	Preoxygenation with Optiflow™ – the effect of speech on lung oxygenation.
Study Design	Randomised controlled trial
Study Participants	Elective booked surgical patients having a general anaesthetic
Planned Size of Sample	28
Follow up duration	none
Planned Study Period	Sept 2018 to January 2019
Research Question/Aim(s)	If a patient speaks during the process of preoxygenation with high-flow nasal oxygen via the Optiflow™ system, is the efficacy reduced as measured by end-tidal lung oxygen content?

FUNDING AND SUPPORT IN KIND

FUNDER(S)	FINANCIAL AND NON FINANCIAL SUPPORT GIVEN
Fisher & Paykel Healthcare Limited [name] United Kingdom	F&P have given free disposable equipment for use in this and other research studies.

ROLE OF STUDY SPONSOR AND FUNDER

[figure not shown]
PROTOCOL CONTRIBUTORS

[name] and [name] (medical student) are responsible for the study design, conduct, data analysis and interpretation, manuscript writing, and dissemination of results.

The sponsor and equipment provider do not control the final decision regarding any of these aspects of the study.

KEY WORDS:	Preoxygenation
	Optiflow™
	End-tidal oxygen

STUDY FLOW CHART

Optiflow™ device removed and subject released from study

STUDY PROTOCOL

Preoxygenation with high-flow nasal oxygen using Optiflow™ - does speech have an effect on endtidal oxygen achieved when compared to closed-mouth nasal breathing?

1 BACKGROUND

Before anaesthetists commence anaesthetising patients it is common practice in many cases to ask the patient to breathe 100% oxygen for a few minutes (this is called preoxygenation). The reason for this is that the percentage of oxygen in the lungs can be raised from about 21% to 90%. If / when patients stop breathing as the anaesthetic drugs are injected, the oxygen in the lungs acts as a reservoir to keep them well oxygenated whilst the anaesthetist inserts a breathing tube into the airway. If this process of intubating the airway proves to be difficult and prolonged (e.g. due to anatomical problems) the preoxygenation will have given a larger reservoir of oxygen in the lungs and the patient will be less likely to become poorly oxygenated and come to harm.

Preoxygenation can be done with a normal anaesthetic circuit or with other oxygen delivery equipment such as high-flow nasal oxygenation with the Optiflow™ device. The latter is commonly used to support awake patients with breathing difficulties but is increasingly used in anaesthesia to maintain a high flow of oxygen via a patient's nasal airway and may be useful to prevent falls in oxygen levels during difficult intubation of the airway.

The amount of oxygen in the lungs after a period of preoxygenation can readily be measured with standard anaesthetic monitoring equipment.

Preoxygenation is commonly done with the patient breathing through their nose with a closed mouth. However, people often tend to talk during this process and this may result in less efficient preoxygenation if they breathe in room air whilst doing so.

This study aims to investigate whether there is a measurable difference in the efficiency of Optiflow™ preoxygenation (as measured by expired oxygen content) when the patient either breaths only through their nose or when they talk during the process. Talking will be standardised by reading aloud a poem.

2 RATIONALE

During induction of anaesthesia, one of the primary aims of the anaesthetist is to continue to keep the patient well oxygenated whilst the patient passes from the situation of breathing for them self to being anaesthetised and having their breathing controlled or supported by the anaesthetist. This will often entail a period of time when from when the patient stops breathing (an apnoeic period) until an airway device is inserted and the anaesthetist can oxygenate the lungs. If that apnoeic period is prolonged, the amount of oxygen remaining in the lungs will start to fall and this will result in a fall in the amount of oxygen in the bloodstream and then the oxygenation of vital organs. To try to prevent this happening it is common practice to increase the oxygen content in the lungs before the patient is anaesthetised by asking them to breathe 100% oxygen for a short period of time (about 3 minutes) before the start of the anaesthetic. Research has shown that the amount of oxygen in the lungs can be raised to 85-90% by this process – an increase to over 4 times the usual amount – which will allow the patient to remain well oxygenated for several minutes without breathing.

An alternative technique which can be used alongside preoxygenation is to use high-flow nasal oxygenation (in which a high flow of warmed, humidified oxygen is provided from nasal prongs) to keep oxygenating the lungs during a period of apnoea. It has been possible to continue oxygenating

apnoeic patients for up to 30 minutes during airway surgery using such a technique but this can only happen if the airway from nose/mouth through the larynx and into the trachea remain open and patent.

It is therefore becoming common practice to use a device such as Optiflow™ to perform both preoxygenation and apnoeic oxygenation since the device can remain in place from the start of preoxygenation until the airway has been secured and hopefully extend the safe apnoeic period in those cases where the anaesthetist has either expected or unexpected difficulty in passing an endotracheal tube.

Despite the value of high-flow nasal oxygenation during apnoea, preoxygenation remains important because, if the airway become not fully patent (a not uncommon situation in anaesthesia) the highflow nasal oxygenation becomes ineffective and then we become reliant on the oxygen stores already produced by preoxygenation to prevent falls in systemic oxygenation and potential patient harm.

In circumstances when we are using Optiflow™ to provide preoxygenation it is important that the patient breathes 100% oxygen into their lungs. If they start to speak during the process there is the possibility that they might breath in some room air through their mouth despite the high flow of oxygen via their nose. If they dilute the inspired oxygen in this manner it may be that the lung oxygen content at the end of preoxygenation is not as high as it might otherwise be and the safe apnoeic period will therefore be shorter.

By measuring the expired lung oxygen content after Optiflow™ preoxygenation in groups with either solely nasal breathing or with speech encouraged we hope to quantify any difference in efficacy. Publication of this information may help to guide clinical practice especially if a large difference in mean values between the 2 groups is demonstrated.

3 THEORETICAL FRAMEWORK

Previous studies including those involving the principal investigator have shown that the end tidal oxygen content of the lungs can be reliably measured by asking a subject to exhale and then breathe normally via a mouthpiece which has a side sampling port connected to a standard gas monitor (as used during anaesthesia) which will measure and display the expired oxygen percentage.

We have also shown that Optiflow™ can preoxygenate volunteer females to a comparable level to traditional facemask oxygenate within 3 minutes. In that trial all subjects breathed through their nose with a closed mouth and no vocalisation.

The planned study moves on from previous studies by comparing 2 groups of subjects (patients not volunteer medical students) who either breathe with a closed mouth or recite a standardised text, reading from a sheet. The study is designed to address the gap in knowledge about whether speech adversely affects the efficacy of this preoxygenation technique.

4 RESEARCH QUESTION

The research question being addressed is: Does speaking during preoxygenation with Optiflow™ have an effect on the expired oxygen fraction in the lungs at the end of 3 minutes preoxygenation.

4.1 Objectives

The objective is to quantify the end-tidal oxygen after 3 minutes of Optiflow™ preoxygenation in groups of either closed-mouth, nasal breathers or ones who speak throughout the process.

4.2 Outcome

The outcome will be that we will produce a mean (range/SD) value for the end-tidal oxygen content of the lungs after 2 styles of Optiflow™ preoxygenation. We can give guidance to the practical use of high-flow nasal oxygen for preoxygenation particularly with respect to whether efficacy is improved if patients are instructed to refrain from talking during the process.

5 STUDY DESIGN and METHODS of DATA COLLECTION AND DATA ANALYSIS

For each subject demographic data will be collected: age, gender, height, weight, body mass index.

For both study group arms, the end tidal oxygen fraction of the first expired breath after 3 minutes of preoxygenation will be recorded.

Demographic data will be analysed with descriptive statistics.

The findings generated (mean end-tidal oxygen levels) will be quantitative/parametric data and a t-test will be used to compare the groups.

Data will be anonymised and stored on password protected NHS computers.

Access to the study data will only be available to the researchers.

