7.2 Sampling

7.2.1 Size of sample

A power calculation has been performed which gives a sample size of 28 (estimated mean for control group 0.85, estimated mean for test group 0.75 {SD 0.1}, p=0.05, power 0.8 [actual power 0.824]).

The control group value comes from a previous volunteer study using the same technique. The lower mean value for the speech group is a conservative estimate based on experience with mask preoxygenation by the chief investigator.

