## Statistical Analysis Plan

### ***Methods of randomisation***

Participants were randomly allocated to the either the speech or non-speech arm of the study according to a random number generator and a key drawn up prior to randomisation. This was done following the consent and recruitment process to maintain allocation concealment. Figure 3. demonstrates the randomisation of participants.

Number Generated	Assigned Group
Odd	Speech
Even	Non-speech

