**Figure 3: A reference table to randomly allocate participants to both arms of the study.**

### ***Power calculations***

The primary outcome measure was ETO2 after 3 minutes of oxygen via the Optiflow™ device. In order to ascertain a sample size, data was taken from a previous study by J. Powell and [name] showing that an ETO2 of 0.85 could be achieved using the Optiflow device without speech. An estimate for the speech group was then decided (rendering an ETO2 of 0.75, SD= 0.1) based off detecting a minimally significant difference. The sample size was generated by 'G\*Power' software. This yielded a sample size of 28 whereby  $\alpha=0.05$  and  $1-\beta=0.8$ . An unpaired t-test was performed, and all statistical analysis was carried out using GraphPad Prism 8.

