### ***Statistical Analysis***

The data was imported from an excel spreadsheet into GraphPad Prism 8. Prior to analysis, some normality tests were run to determine whether the data was parametric or non-parametric. 18 participants in the 'Speech' group and 12 participants in the 'Non-Speech' group were included in the analysis using parametric statistics for normally distributed data. The confidence intervals were set at 95% and a P value of  $<0.05$  was used to confirm any statistical significance.

An unpaired t-test was then conducted to investigate the likelihood that the difference between the means had been caused by chance. This would help establish a relationship between ETO2 achieved at the end of three minutes between those in the speech arm compared against those in the non-speech arm.

To determine demographics, the mean (standard deviation) was used to calculate average age, whilst median and Interquartile range were used as a measure of distribution for BMI and height.

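### Should BMI, which is recorded for every patient but only summarised, have been adjusted for when end-tidal oxygen is compared?

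*Protocol*

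**What the plan says.** Protocol section 5 lists the baseline data: "For each subject demographic data will be collected: age, gender, height, weight, body mass index". It gives them one use: "Demographic data will be analysed with descriptive statistics". For end-tidal oxygen it says that "a t-test will be used to compare the groups".

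The SAP agrees. Under Statistical Analysis, "median and Interquartile range were used as a measure of distribution for BMI and height", and the between-arm comparison is the unpaired t-test: "An unpaired t-test was then conducted to investigate the likelihood that the difference between the means had been caused by chance". Under Methods of randomisation, "Participants were randomly allocated to the either the speech or non-speech arm of the study according to a random number generator"; odd numbers go to speech and even numbers to non-speech, with no stratification described.

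Neither document plans an adjusted estimate, says that any baseline variable predicts end-tidal oxygen, or reports an imbalance between the arms. Neither says whether the demographic summary is by arm or pooled.

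**The concern.** The trial is small: 28 planned (protocol section 7.2.1) and 18 plus 12 analysed (SAP, Statistical Analysis). Entry is open to BMI 18 to 35 (protocol section 7.1.1), and simple randomisation leaves BMI balance to chance. At this size the arms' mean BMI would differ by more than half an SD in about 18 to 19% of trials by chance alone.

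If BMI is related to end-tidal oxygen, a linear model with BMI as a covariate would remove part of the residual variance and allow for any chance imbalance. That would cost one degree of freedom and use data already held. The aim in protocol section 4.1 is to quantify end-tidal oxygen in the two groups, so a wider interval than necessary would matter. On that view the plan throws away precision.

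**Working it through.** **Inputs.** Means 0.85 and 0.75 and SD 0.1, so the standardised difference is d = 0.10/0.1 = 1.0; alpha 0.05; N = 28; stated power 0.824 (all protocol section 7.2.1). Analysed: 18 speech, 12 non-speech (SAP, Statistical Analysis). The within-arm R² between BMI and end-tidal oxygen is in neither document, so it is an assumption, shown from 0 to 0.30.

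**The plan's own figure.** For 14 per arm the noncentrality is 1.0/√(1/14 + 1/14) = 2.646 on 26 df. One-sided 0.05 gives power 0.824, which matches the stated figure. Two-sided 0.05 gives 0.721. The sidedness behind N = 28 is a separate question, and a covariate should not be brought in to repair it. Two-sided figures are used below.

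**Validity.** Under random allocation the expected BMI difference between arms is zero. Chance differences in BMI, and any effect they have on the outcome, are already part of the within-arm variance in the standard error of the t-test. The test therefore keeps its 5% level without adjustment; simulation under the null gives 0.050.

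**Precision with 18 and 12.**
- Unadjusted: half-width = t(0.975, 28) × 0.1 × √(1/18 + 1/12) = 2.048 × 0.1 × 0.3727 = 0.0763. Power is 0.736.
- Adjusted for one covariate: 27 df. The variance is multiplied by (1 − R²) × (N − 3)/(N − 4) = (1 − R²) × 27/26, where 27/26 is the average penalty for chance imbalance. At R² 0.20 this is 0.80 × 1.0385 = 0.831, so half-width = 2.052 × 0.1 × 0.3727 × √0.831 = 0.0697.

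| Assumed R² | Power | 95% CI half-width | Change in half-width |
|---|---|---|---|
| none (t-test) | 0.736 | 0.0763 | – |
| 0 | 0.719 | 0.0779 | +2.1% |
| 0.05 | 0.740 | 0.0760 | −0.4% |
| 0.10 | 0.763 | 0.0739 | −3.1% |
| 0.20 | 0.810 | 0.0697 | −8.7% |
| 0.30 | 0.858 | 0.0652 | −14.5% |

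Break-even R² is 1 − (2.0484/2.0518)² × 26/27 = 0.040, a correlation of about 0.20.

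**One trial rather than the average.** In 40,000 simulated trials with 14 per arm, the adjusted interval was the narrower one in 20%, 39%, 61%, 83% and 94% of trials at R² 0, 0.04, 0.1, 0.2 and 0.3. At R² 0.04 with 18 and 12 it was about 40%. A better-than-even chance of a narrower interval needs R² of roughly 0.07.

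**Cost of a second estimate.** Each analysis alone has type I error of 0.05. If the smaller of the two p-values is taken, it is about 0.058 when R² is 0 and about 0.065 to 0.075 over the R² values at which adjustment helps. Choosing among the t-test and five single-covariate models, one for each recorded variable, gives about 0.08 when none is prognostic.

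**The case for a change.** The strongest case for adjusting is that the trade is lopsided: about 2 points of power and a 2% wider interval if BMI is irrelevant, against an interval about 9% narrower at R² 0.20, for one extra regression. The t-test could stay primary, the model could be limited to one covariate and reported whichever way it falls, and a BMI summary by arm would let readers judge comparability.

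The arithmetic stands, and so does the general principle that adjusting for a strongly prognostic baseline variable fixed in advance is good practice. What is missing is any ground in the documents for treating BMI as such a variable. Five variables are listed on equal terms, and nothing singles BMI out. Entry is limited to BMI 18 to 35 and ASA 1 and 2, and restricting a covariate's range generally weakens its correlation with the outcome, so R² of 0.2 or 0.3 cannot be presumed.

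Timing matters too. The SAP is in the past tense and gives the numbers analysed, so a model added now would most likely be post hoc and secondary. The tabulated power gains would not reach the trial's own test. The by-arm summary is a fair reporting suggestion, but the plan's silence on layout is not a statement that the summary is pooled.

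**Conclusion.** The concern does not hold. The protocol and SAP agree with each other, the unadjusted t-test is valid under the random allocation described, and no promised analysis is missing. With 18 and 12 patients, BMI adjustment would move the CI half-width from 0.076 to somewhere between 0.078 (R² 0) and 0.065 (R² 0.30). Where in that range it falls depends on a figure that neither document gives. Against that possible gain stands a choice between two p-values, which would raise type I error above 5% if it were exploited. Experienced statisticians could reasonably choose either way.

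This rests on the SD of 0.1 and difference of 0.10 in protocol section 7.2.1, a two-sided 5% test, a linear BMI effect that is the same in both arms, and allocation carried out as the SAP describes. It concerns only the absence of covariate adjustment and does not settle whether 28 patients were enough.

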6 STUDY SETTING

The study will be a single centre study at University Hospital Southampton.

The study will be conducted in the operating theatre anaesthetic room prior to anaesthesia and surgery.

Participants will have been recruited from the patients booked on the elective surgical list who have been to the preassessment clinic in advance of the operating day.

7 SAMPLE AND RECRUITMENT

7.1 Eligibility Criteria

The study population will be from booked, elective surgical patients who have been preassessed and given a patient participation sheet to read in advance.

7.1.1 Inclusion criteria

Age 18 to 65

ASA category 1 and 2 for cardiorespiratory fitness

BMI 18 to 35

Able to understand instructions and read aloud in English

7.1.2 Exclusion criteria

ASA 3 or above for cardiorespiratory fitness

Outside age or BMI range

Unable to understand and follow detailed instructions from the researcher.

Inability to read aloud the standardised poem.

Prescribed a sedative premedication.

7.2 Sampling

7.2.1 Size of sample

A power calculation has been performed which gives a sample size of 28 (estimated mean for control group 0.85, estimated mean for test group 0.75 {SD 0.1}, p=0.05, power 0.8 [actual power 0.824]).

The control group value comes from a previous volunteer study using the same technique. The lower mean value for the speech group is a conservative estimate based on experience with mask preoxygenation by the chief investigator.

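### The sample size of 28 and the stated power of 0.824 fit a one-sided 5% t-test; on the two-sided analysis the documents indicate, planned power is about 72%

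*Protocol*

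**What the plan says.** Protocol section 7.2.1 gives a total of 28, a control mean of 0.85, and then "estimated mean for test group 0.75 {SD 0.1}, p=0.05, power 0.8 [actual power 0.824"]. The SAP, under Power calculations, uses the same means and SD, names G*Power and an unpaired t-test, and says "This yielded a sample size of 28 whereby" alpha is 0.05 and power 0.8. Protocol section 5 says only that "a t-test will be used to compare the groups". None of these places states the number of tails, and no target per group is given.

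The rest of the wording is mixed:

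- **Neutral.** The title asks about an effect. Section 4 asks whether speaking will "have an effect on the expired oxygen fraction in the lungs". In section 2, "we hope to quantify any difference in efficacy".
- **Directional.** The study summary asks "is the efficacy reduced as measured by end-tidal lung oxygen content". Section 1 says of talking that "this may result in less efficient preoxygenation". Section 3 speaks of an adverse effect of speech, and section 4.2 asks whether efficacy improves when patients do not talk.
- **Analysis rule.** The SAP, under Statistical Analysis, says "The confidence intervals were set at 95% and a P value of" less than 0.05 was used for significance.

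**The concern.** A power figure describes one particular test. If the calculation was one-sided and the analysis two-sided, the stated power does not belong to the analysis. A reader who sees 95% intervals and P<0.05 will assume a conventional two-sided test and credit it with 80 to 82% power. If the true figure is 72%, the planned chance of missing a difference of 0.10 is 28%. A non-significant result would then be taken as stronger evidence of no effect than it is. That matters here because section 4.2 intends the result to guide whether patients are told not to talk.

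**Working it through.** **Inputs**

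- Means 0.85 and 0.75, SD 0.1, alpha 0.05, target power 0.80, stated power 0.824, total 28 (Protocol 7.2.1; repeated in the SAP except for 0.824).
- Unpaired t-test (SAP, Power calculations).
- Assumption: the single SD of 0.1 applies to both groups.
- Assumption: equal groups of 14. No per-group target is given; the odd/even randomisation key implies 1:1 on average.

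**Formula.** Standardised difference d = (0.85 − 0.75)/0.1 = 1.0. For groups n1 and n2, the test statistic follows a noncentral t distribution with n1 + n2 − 2 degrees of freedom and noncentrality d × √(n1·n2/(n1 + n2)). With 14 and 14 this gives 26 degrees of freedom and noncentrality √7 = 2.646.

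**Step 1: reproduce the stated figure.** One-sided 5%, critical value 1.706: power = 0.8241. With 13 per group it is 0.797, so 14 is the smallest equal group size that reaches 0.80. Both the 28 and the 0.824 are matched.

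**Step 2: the two-sided test.** Two-sided 5%, critical value 2.056: power = 0.7214, so the type II error is 1 − 0.721 = 0.279.

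**Step 3: what 80% power would take, two-sided.** With 16 per group power is 0.781; with 17 it is 0.807. The total needed is 2 × 17 = 34. With 14 per group, 80% power needs d = 1.100, a difference of 1.100 × 0.1 = 0.11.

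**Step 4: does an unequal split of 28 explain the figure?**

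| Split | One-sided | Two-sided |
|---|---|---|
| 14/14 | 0.824 | 0.721 |
| 13/15 | 0.822 | 0.719 |
| 12/16 | 0.817 | 0.713 |

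No split brings the two-sided power near 0.824. Reading 28 as the number per group gives 0.957 two-sided, which does not match either.

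**Step 5: the matching interval.** The two-sided alpha that gives 0.824 with 14 per group is 0.10. That test pairs with a 90% interval, not the SAP's 95% interval.

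**Step 6: dependence on the SD** (common to both groups, two-sided 5%, 14 per group).

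| SD | Power |
|---|---|
| 0.09 | 0.808 |
| 0.10 | 0.721 |
| 0.11 | 0.639 |
| 0.12 | 0.565 |

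Power reaches 0.80 only if the SD is at most 0.1/1.100 = 0.091.

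**The case against.** Four points can be made for the plan.

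1. **The SD may not be common.** It is printed once, next to the speech mean, and no control SD is given. If the control SD were about 0.074 (an assumption), the root-mean-square SD would be √((0.1² + 0.074²)/2) ≈ 0.088, and a two-sided 5% test with 14 per group would have power close to 0.824. This is arithmetically possible. It needs a control SD that appears in neither document, whereas a common SD of 0.1 with a one-sided test gives 0.824 to three decimals from the printed figures alone. It remains the less likely explanation, but the assumption of a common SD should be stated.

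2. **A one-sided test may have been meant.** Several sentences are directional, and the mechanism described, dilution by room air, can only lower end-tidal oxygen. P<0.05 alone does not settle the number of tails, and a 95% interval can be reported beside a one-sided test. So the two-sided analysis is an inference. If one-sided was intended, 28 is correct and the calculation contains no error. The number of tails would still be undeclared, and the 95% interval would still not match the test that was powered.

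3. **More patients were analysed.** The SAP reports 18 and 12, 30 in all. Under the same planning assumptions that split gives 0.736 two-sided, so it does not close the gap.

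4. **The effect is small.** The detectable difference moves from 0.10 to 0.11, on an SD without a stated source, and no result changes. This limits the seriousness. It does not make the stated power right for the indicated analysis.

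**Conclusion.** The concern holds. The total of 28 and the power of 0.824 are those of a one-sided 5% unpaired t-test, a choice declared nowhere. On the two-sided 5% analysis that the SAP's intervals and the main research question indicate, planned power is 72%, about 10 percentage points below the stated figure and 8 below the target. This rests on SD 0.1 in both groups, equal groups of 14, and reading the analysis as two-sided. The defect lies in the statement of power and in the undeclared number of tails. It does not affect the validity of the estimate, the interval or the P value. It should be fixed.

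**What to change.** In Protocol 7.2.1 and in the SAP under Power calculations and Statistical Analysis, state that the t-test is two-sided at 5%, and replace the power statement with wording such as:

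> With 28 patients (14 per group) and an SD of 0.1 in both groups, a two-sided 5% t-test has 72% power to detect a difference of 0.10. The difference detectable with 80% power is 0.11.

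As the analysis has already been described, make this a dated correction, and report the tail setting and SDs used in the G*Power run if they were kept. For the 18 and 12 analysed, keep the 95% confidence interval as the measure of precision and add no retrospective power. Use a one-sided test only if dated evidence shows it was chosen before the data were seen, and then bring the interval and the P-value rule into line with it.

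The cost is about two sentences in each document. No patient need be added and no analysis rerun. The only downside is a less favourable stated power.

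### Do the differing reasons for the 0.10 planning difference, and the lack of a stated threshold for reading the confidence interval, call for a change to the plan?

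*Protocol*

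**What the plan says.** **Planning figures.** Protocol section 7.2.1 gives "estimated mean for control group 0.85, estimated mean for test group 0.75 {SD 0.1}, p=0.05, power 0.8 [actual power 0.824", for a total of 28 patients. The SAP, under Power calculations, repeats the two means, the SD and the total.

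**Reason for 0.75.** The protocol's reason is: "The lower mean value for the speech group is a conservative estimate based on experience with mask preoxygenation by the chief investigator". The SAP calls 0.75 an estimate too, but says it was "based off detecting a minimally significant difference".

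**Use of the result.** Protocol section 4.1 sets an objective of quantifying end-tidal oxygen in the two groups. Section 4.2 names a mean with range or SD as the outcome and adds: "We can give guidance to the practical use of high-flow nasal oxygen for preoxygenation". Section 2 says publication may help guide practice, "especially if a large difference in mean values between the 2 groups is demonstrated", without giving a size.

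**Analysis.** Both documents specify an unpaired comparison of means by t-test. The SAP, under Statistical Analysis, states "The confidence intervals were set at 95% and a P value of" less than 0.05 as its criteria. It also reports that "18 participants in the 'Speech' group and 12 participants in the 'Non-Speech' group were included in the analysis".

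**The concern.** The two reasons give 0.10 different roles. An estimate drawn from experience describes what the investigators expected to see. A minimal difference describes what they would not want to miss. If 0.10 is only the expected loss, the trial was not sized for a smaller loss that might still matter. If 0.10 is the smallest loss that matters, an interval covering both 0 and 0.10 settles nothing.

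The plan also hopes to advise on whether patients should be told not to talk, yet gives no rule for moving from an interval to advice. With about 30 patients, a reader could take p > 0.05 to mean that talking does no harm when the data could not show that. Section 2 of the protocol links lower lung oxygen to a shorter safe apnoeic period, so such a misreading could affect practice.

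**Working it through.** **1. The plan's own figure.** Inputs from protocol 7.2.1: difference 0.85 − 0.75 = 0.10, SD 0.10, so the standardised difference is 1.0; 14 per arm; alpha 0.05. Power from the noncentral t distribution with 26 degrees of freedom:

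- one-sided test: 0.8241, matching the stated 0.824;
- two-sided test: 0.721, with 17 per arm (34 in total) needed for 80% (0.807).

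Neither document states whether the test is one- or two-sided. That is a separate question. The figures reproduce under either justification of 0.10, because the calculation uses only the size of the difference.

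**2. The two reasons side by side.**

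| | Protocol 7.2.1 | SAP, Power calculations |
|---|---|---|
| Non-speech mean | 0.85, from a previous volunteer study | 0.85, from a previous study |
| Speech mean | 0.75 | 0.75 |
| SD | 0.1 | 0.1 |
| Total | 28 | 28 |
| Reason for 0.75 | conservative estimate from mask experience | minimal difference to be detected |

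Only the last row differs. In its usual sense, a conservative estimate of a loss sits at the low end of what is expected. A value chosen that way can also serve as the smallest difference the trial is built to detect, so the rows do not contradict each other.

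**3. Width of the planned interval.** Half-width = t(0.975, df) × SD × √(1/n₁ + 1/n₂), at SD 0.10:

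- 14 and 14: 2.0555 × 0.10 × 0.3780 = 0.0777;
- 18 and 12: 2.0484 × 0.10 × 0.3727 = 0.0763.

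A result just short of two-sided significance has a lower limit at about 0 and an upper limit at about twice the half-width, taking the sample SD equal to the assumed SD:

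| SD | 14 and 14 | 18 and 12 |
|---|---|---|
| 0.10 (documents) | 0.155 | 0.153 |
| 0.07 (assumed) | 0.109 | 0.107 |
| 0.05 (assumed) | 0.078 | 0.076 |

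**4. How often a non-significant interval would include 0.10.** Simulation of 400,000 trials per row, 18 and 12 analysed, two-sided 95% interval. The true losses of 0 and 0.05 are assumptions; the documents give neither.

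| True loss | SD | Non-significant | Of those, interval includes 0.10 |
|---|---|---|---|
| 0.05 | 0.10 | 75% | 66% |
| 0.05 | 0.07 | 54% | about 25% |
| 0.05 | 0.05 | 26% | under 1% |
| 0 | 0.10 | 95% | 25% |
| 0 | 0.07 | 95% | about 3% |
| 0 | 0.05 | 95% | under 1% |

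At a true loss of zero and SD 0.10, about 74% of all intervals have an upper limit below 0.10. The non-significant column treats p > 0.05 as a two-sided 95% interval covering 0. A one-sided test would change that column and the shares, but not the half-widths.

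**5. What a change would alter.** Stating the role of 0.10 and adding a sentence on non-significant results leaves the sample size, test, interval and significance criterion as they are. A threshold would be new content, but nothing in the documents supplies a clinical basis for one. Since the SAP already reports the numbers analysed, any threshold added now would be post hoc.

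**The case for a change.** The strongest case for acting is that the role of 0.10 governs how an inconclusive result should be read, and the documents leave it open. The SAP's phrase does not say whether it means clinical or statistical significance, and the protocol's reason comes from a different delivery method. The guidance question has two possible answers, yet the plan's criteria speak only to one. At the documents' own SD, a true loss of 0.05 would give p > 0.05 in about three trials out of four, and about two-thirds of those intervals could not exclude 0.10. Sizing the trial for 0.05 would have taken 102 patients (one-sided) or 128 (two-sided). Clarifying the wording would need no new data.

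The ambiguity of wording stands, and so does the arithmetic. The consequence does not stand as firmly. The figure of two-thirds, like the totals of 102 and 128, depends on a true loss of 0.05 that appears nowhere in the documents, and the proportion drops sharply at a true loss of zero or a smaller SD. The plan sets out to estimate a difference between means and claims neither equivalence nor non-inferiority, so a margin is not a required element. The misreading feared is one that no passage proposes.

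**Conclusion.** No change is needed. The two documents word the reason for 0.10 differently but agree on every planning figure, and the reasons are compatible. Following the plan as written yields a valid t-test and a 95% interval.

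What is left is a gap that analysts fill as a matter of course. The natural reading of the SAP is that the interval is for the difference in means. A report giving that interval (non-speech minus speech) shows which losses remain plausible, and ordinary practice is not to infer absence of effect from p > 0.05 alone. At SD 0.10 the half-width of about 0.08 makes that caution worth keeping in mind; at SD 0.05 a result just short of significance would have an upper limit near 0.08, already below 0.10.

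This conclusion rests on three things: the plan claims no equivalence, no passage treats a null result as reassurance, and the planning figures are the same in both documents. It does not cover whether the power calculation was one- or two-sided.
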